7.0 Vulnerable Populations

If the research involves special populations that are considered vulnerable, describe the safeguards included to protect their rights and welfare.

NOTE: You should refer to the appropriate checklists, referenced below, to ensure you have provided adequate detail regarding safeguards and protections. You do not, however, need to provide these checklists to the IRB.

7.1 For research that involves **pregnant women**, safeguards include:

NOTE CHECKLIST: Pregnant Women (HRP-412)

Response:

There is no possible harm on the pregnancy due to assessing daytime sleepiness before and after the intervention, and using paper survey/interview procedures so no additional procedures are needed for their protection.

N/A: This research does not involve pregnant women.

7.2 For research that involves **neonates of uncertain viability or non-viable neonates**, safeguards include:

NOTE CHECKLISTS: Non-Viable Neonates (HRP-413), or Neonates of Uncertain Viability (HRP-414)

Response:

Not applicable: This research does not involve non-viable neonates or neonates of uncertain viability.

N/A: This research does not involve non-viable neonates or neonates of uncertain viability.

7.3 For research that involves **prisoners**, safeguards include:

NOTE CHECKLIST: Prisoners (HRP-415)

Response:

Not applicable: This research does not involve prisoners.

N/A: This research does not involve prisoners.

7.4 For research that involves **persons who have not attained the legal age for consent to treatments or procedures involved in the research (“children”)**, safeguards include:

NOTE CHECKLIST: Children (HRP-416)

Response:

Not applicable: This research does not involve persons who have not attained the legal age for consent.

N/A: This research does not involve persons who have not attained the legal age for consent to treatments or procedures (“children”).

7.5 For research that involves *cognitively impaired adults*, safeguards include:

NOTE CHECKLIST: Cognitively Impaired Adults (HRP-417)

Response:

Not applicable: This research does not involve cognitively impaired adults.

N/A: This research does not involve cognitively impaired adults.

7.6 Consider if other specifically targeted populations such as students, employees of a specific firm, or educationally or economically disadvantaged persons are vulnerable. Provide information regarding their safeguards and protections, including safeguards to eliminate coercion or undue influence.

Response:

Not applicable: This research does not involve these populations.

8.0 Eligibility Screening

8.1 Describe *screening procedures* for determining subjects' eligibility. Screening refers to determining if prospective participants meet inclusion and exclusion criteria.

 *Include all relevant screening documents with your submission (e.g. screening protocol, script, questionnaire).*

Response: Screening for inclusion criteria includes a YES response to the following questions:

Are at least 18 years of age?

Insomnia Severity Index>7 and/or Holland Sleep Disorders Screening Questionnaire>4.0

Do you have a diagnosis of breast, colorectal, or prostate cancer stage I, II or III; or lung cancer stage I-IV?

Have you had your cancer surgically removed at least 1-month ago?

Has it been more than one month since you completed cancer treatment (except for hormone treatment or maintenance targeted therapies)?

Screening for exclusion criteria includes a NO response to the following questions:

Do you have sleep disorders other than insomnia or obstructive sleep apnea who are CPAP-compliant => 4-hours/night use?

Do you have any poorly managed medical/psychiatric illnesses, fibromyalgia, or a history of seizures?

Are you currently exceeding alcohol or abusing drugs?

Do you engage in shift work or traveled >1 time zone past month?

Are you able to wear an actigraph on your non-dominant wrist?

1. The PI or Study Coordinator will use the Recruitment Script and Participant Eligibility Screening Form (instruments attached) to screen all eligible participants and the Holland Sleep Disorders Questionnaire (HSDQ), a valid, reliable and accurate diagnostic measure based on the International Classification of Sleep Disorder (ICSD-2) to determine the presence of insomnia, sleep apnea or any other sleep disorder. Depending on the scores, participants will be enrolled, require additional screening (sleep apnea) or referred to their provider for additional sleep disorders diagnoses.
2. Individuals who screen positive for sleep apnea and insomnia will be invited to wear the small portable ApneaLink Plus device overnight for one night in their home to screen for sleep apnea before continuing in the study. All results of the ApneaLink Plus overnight studies will be reviewed by Drs. [name] (consultant) and [name] (PI) after electronic scoring. Participants with moderate-severe sleep apnea (≥ 15 episodes/hour) will be referred for further evaluation and possible positive airway pressure treatment. Patients with moderate-severe sleep apnea will not be recruited in the proposed study.
3. If a participant's result to the screening indicate that they are not eligible, they will be thanked for their interest and provided 2 copies of the ApneaLink Plus report: one for themselves and a copy for their provider.

In addition, Buffalo Research Registry, Research Match, and i2b2 have been added to screen for eligible participants. For i2b2, the Institute of Healthcare Informatics team will provide contact information for the eligible participants. The provider will be contacted for approval using the Physician Permission Letter (draft letter attached). If the provider does not object, patients will be contacted by mail (draft letter attached) and then by telephone. As a result of HRP-611 Partial HIPAA Waiver, we will prescreen clinic patients at Roswell Park Comprehensive Cancer Center.

N/A: There is no screening as part of this protocol.

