6.0 Inclusion and Exclusion Criteria

6.1 *Describe the criteria that define who will be **included** in your final study sample.*

NOTE: This may be done in bullet point fashion.

Response:

1. Age \geq 18 years of age
2. \geq 1-month from surgery and \geq 1-month from any other treatment (except for hormone treatment or maintenance targeted therapies) for stages I through III: breast, colorectal, and prostate cancers and stages I through IV: lung cancer.
3. Meet published criteria for chronic insomnia: sleep latency $>$ 30 minutes or wake after sleep onset of $>$ 30 mins for \geq 3 nights/week for at least 1-month
4. ApneaLink Screening Apnea Hyponea Index $<$ 15

5. Ability to complete data collection instruments

6.2 *Describe the criteria that define who will be **excluded** from your final study sample.*

NOTE: This may be done in bullet point fashion.

Response:

1. Other pre-existing sleep disorders except insomnia or obstructive sleep apnea who are CPAP-compliant => 4-hours/night use
2. Unstable medical or psychiatric illness, fibromyalgia, history of seizures, current substance abuse
3. Engaged in night or rotating shift work
4. Travel across two or more time zones within 1 month prior to study participation
5. Inability to complete data collection measures independently
6. Individuals with conditions affecting the non-dominant arm (use of wrist actigraph)

6.3 *Indicate specifically whether you will include any of the following special populations in your study using the checkboxes below.*

NOTE: Members of special populations may not be targeted for enrollment in your study unless you indicate this in your inclusion criteria.

Response:

Not applicable: None of the following special populations will be recruited in the current study.

- Adults unable to consent
- Individuals who are not yet adults (infants, children, teenagers)
- Pregnant women
- Prisoners

6.4 *Indicate whether you will include non-English speaking individuals in your study.*

Provide justification if you will exclude non-English speaking individuals.

*In order to meet one of the primary ethical principles of equitable selection of subjects, non-English speaking individuals may **not** be routinely excluded from research as a matter of convenience.*

In cases where the research is of therapeutic intent or is designed to investigate areas that would necessarily require certain populations who may not speak English, the researcher is required to make efforts to recruit

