10.0 Procedures Involved

10.1 *Provide a description of **all research procedures or activities** being performed and when they are performed once a subject is screened and determined to be eligible. Provide as much detail as possible.*

NOTE: This should serve as a blueprint for your study and include enough detail so that another investigator could pick up your protocol and replicate the research. For studies that have multiple or complex visits or procedures, consider the addition of a schedule of events table in in your response.

Response:

Following informed consent, in order to rule-out sleep apnea as a confounder, all eligible participants will be offered screening for sleep apnea with the ApneaLink Plus for one night. Following a negative screen for sleep apnea, demographics, diagnoses, treatments, comorbidities, etc. will be extracted from the Electronic Health Record (EHR) using the Medical Record Review Questionnaire (to verify certain self-report data); beliefs about sleep will be determined by Dysfunctional Beliefs and Attitudes about Sleep; mood, anxiety and depression will be measured with Hospital Anxiety and Depression Scale; pain and quality of life will be determined by Functional Assessment of Cancer Therapy-G; sleep quality will be measured with Pittsburgh Sleep Quality Index; daily sleep will be assessed with 7-day sleep diary; objective sleep will be evaluated with 7-day actigraph; fatigue will be assessed with Profile of Mood States; and daytime sleepiness will be determined by the Epworth Sleepiness Scale (Johns 1991).

One week, after baseline assessments, each participant will be randomized by the biostatistician. Participants will then be scheduled for either the brief behavioral therapy for insomnia (BBTI) session (experiment) or the healthy eating program (HEP) session (control). Each intervention is approximately 45-minutes and will be delivered in the clinical setting, online teaching or home.

At the end of the interventions, each participant will be provided weekly sleep diaries to complete for 2-weeks and arrange for 2-follow up telephone calls using the Telephone Follow Up Script (attached). Each telephone contact will begin by reminding participants that their participation is voluntary and they may skip items they wish. Telephone

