Insomnia characteristics Subjective sleep (insomnia severity, sleep quality) Objective sleep (sleep efficiency)	Insomnia Severity Index, Pittsburgh Sleep Quality Index, Sleep diary (daily) Actigraphy-Actiwatch Spectrum Safety emails	X X X	X X X	X X		X X	X
Vulnerability for physical-psychiatric problems Fatigue Sleepiness Disrupted mood Functional status Quality of life	Profile of Mood States Fatigue Subscale Epworth Sleepiness Scale Hospital Anxiety and Depression Scale Functional Assessment of Cancer Therapy-G Functional Assessment of Cancer Therapy-G	X X X X X	X X X X X	X X X X X			X X X X X
Telephone Follow Up	Script		X				
Patient Evaluation Questionnaire	Perceptions of study		X				X

	effectiveness						
--	---------------	--	--	--	--	--	--

10.3 List any instruments or measurement tools used to collect data (e.g. questionnaire, interview guide, validated instrument, data collection form).
 Include copies of these documents with your submission.

Response:

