17.0 Data Management and Analysis

17.1 *Describe the data analysis plan, including any statistical procedures. This section applies to both quantitative and qualitative analysis.*

Response:

Specific Aim 1. The primary analyses involve the statistical assessment of Insomnia Severity Index (ISI) at 1 month and will be based on an analysis of covariance (ANCOVA) model. In taking this approach, we fit the dependent variable as a linear function of independent variables randomized treatment assignment, patient cancer type, the interaction between treatment assignment and cancer type, and baseline ISI level. Rather than utilizing the null distribution associated with the classic F-test for overall treatment differences within the ANCOVA framework, which is dependent on the validity of distributional assumptions, an exact permutation testing approach will be utilized. The randomization mechanism at work is a crucial component in this study in that it will be used to create the randomization distribution by which statistical significance will be determined. For more on this approach see Gail, Tan, and Piantadosi (1988)(120). Reported p-values will be obtained from the permutation distributions of the test statistics based on 10,000 Monte Carlo simulations. As additional analyses, subject covariates will be included as independent variables.

The interaction of treatment group and subject covariates may also be examined in a secondary fashion in order to identify possible differential effects of treatment. The analysis of secondary outcomes will proceed in a similar fashion. All statistical tests will be two-sided and tested at a 0.05 nominal significance level.

Specific Aim 2. Standard multiple regression will be used to determine predictors of efficacious response to BBTI. Standard diagnostic plots will be used to assess model fit and transformations of variables may be considered in order to meet statistical assumptions.

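### The eligibility sections conflict on insomnia, sleep apnea testing and actigraphy, and should be reconciled in one amendment (low severity)

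*Combined protocol and SAP*

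**What the plan says.** **Insomnia.** Section 6.1 item 3 begins "Meet published criteria for chronic insomnia: sleep latency". It asks for latency or wake after sleep onset above 30 minutes, on 3 or more nights a week, for at least a month, and gives no questionnaire score. Section 8.1 introduces its list with "Screening for inclusion criteria includes a YES response to the following questions", and the insomnia item there is "Insomnia Severity Index>7 and/or Holland Sleep Disorders Screening Questionnaire>4.0". That list has no latency, wake, frequency or duration item. Section 8.1 uses the Holland questionnaire (HSDQ) "to determine the presence of insomnia, sleep apnea or any other sleep disorder" and does not say which of its scores the 4.0 refers to.

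**Sleep apnea.** Section 6.1 item 4 makes an ApneaLink index below 15 an inclusion criterion. Section 8.1 invites only people who screen positive for both apnea and insomnia to take the test. Section 10.1 offers it, after consent, to all eligible participants. Section 6.2 item 1 and the 8.1 list make an exception for apnea with adequate CPAP use; 6.1 item 4 does not.

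**Actigraphy.** Section 6.2 item 6 excludes people with a condition of the non-dominant arm. Section 8.1 asks whether the person can wear the device on that wrist, and places the question among those that must be answered NO.

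**Analysis.** Section 17.1 states: "The primary analyses involve the statistical assessment of Insomnia Severity Index (ISI) at 1 month". The model's last terms are "the interaction between treatment assignment and cancer type, and baseline ISI level". Section 10.1 puts baseline before allocation: "One week, after baseline assessments, each participant will be randomized by the biostatistician".

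**The concern.** An entry rule should let two recruiters reach the same decision about the same person. Here they could differ. One who applies 6.1 alone needs no questionnaire score. One who applies the 8.1 list alone needs no latency or wake history. One who applies both enrols a narrower group. The same holds for a person with CPAP-treated apnea, and for a person who screens negative for apnea and so may have no ApneaLink result. A reader of the results could not tell which population was studied.

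The ISI question matters because ISI at 1 month is the primary outcome. The pilot in section 3.1 listed an ISI of at least 8 among its entry conditions. This plan, read literally, sets no minimum for everyone and does not comment on the change. Participants who start low may have less room to improve, which could dilute the treatment difference.

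**Working it through.** **1. The sections compared**

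| Topic | 6.1 / 6.2 | 8.1 | 10.1 |
|---|---|---|---|
| Insomnia | Latency or wake >30 min, ≥3 nights/week, ≥1 month; no score | ISI >7 and/or HSDQ >4.0; no latency or wake item | – |
| ApneaLink | Index <15 required | Only if positive for apnea and insomnia | Offered to all eligible |
| CPAP-treated apnea | Excepted in 6.2 item 1, not in 6.1 item 4 | Excepted in the list; moderate-severe apnea otherwise not recruited | – |
| Actigraph | Arm condition excludes | Being able to wear it must be answered NO | – |

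If 6.1 item 3 and the 8.1 scores both apply, an entrant needs the sleep history plus at least one questionnaire score. ISI of 7 or less with HSDQ above 4.0 still passes. Only reading and/or as *and* would set an ISI minimum for everyone.

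**2. The plan's own sample size**

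Inputs from 17.1 and 17.2: difference 3, SD 4.8, two-sided 0.05, 90% power, 30% dropout. Two-sample t power (noncentral t) is 89.6% at 54 per group and 90.1% at 55, so 55 per group is right. Enrolment is 110/0.7 = 157.1, rounded up to 158. Both figures reproduce.

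**3. What low-ISI entrants could do to power**

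The documents give neither the share *s* of entrants with ISI of 7 or less nor their effect *e* relative to the others. Both are assumed, as is the baseline-outcome correlation *r*.

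- Diluted difference: d = 3 × [1 − s(1 − e)].
- Residual SD for the baseline-adjusted analysis: 4.8 × √(1 − r²), held constant across scenarios. At r = 0.5 this is 4.8 × √0.75 = 4.157.
- No effect (e = 0): s = 10% gives d = 2.70; s = 20% gives d = 2.40.
- Half effect (e = 0.5): s = 10% gives d = 2.85; s = 20% gives d = 2.70.

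Power at 55 per group:

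| r | s = 0 | 10%, e = 0 | 20%, e = 0 | 10%, e = 0.5 | 20%, e = 0.5 | s giving 80% power (e = 0 / e = 0.5) |
|---|---|---|---|---|---|---|
| 0.3 | 92.6% | 86.5% | 77.8% | 89.9% | 86.5% | 18% / 35% |
| 0.5 | 96.3% | 92.2% | 85.1% | 94.6% | 92.2% | 25% / 51% |
| 0.6 | 98.2% | 95.5% | 90.1% | 97.1% | 95.5% | 31% / 62% |
| none (not the planned analysis) | 90.1% | 83.2% | 73.8% | 87.0% | 83.2% | 14% / 28% |

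The last column solves for the difference with 80% power. At r = 0.5 that is 2.241, so s = 1 − 2.241/3 = 25.3% for e = 0, and twice that for e = 0.5.

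**4. At the pilot's effect**

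The pilot difference was 15.07 − 6.94 = 8.13. With 30% of entrants gaining nothing, 0.7 × 8.13 = 5.69, and power exceeds 99.9% at SD 4.8 and at SD 5.27.

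**The case against.** The form gives the two sections different roles. By its template wording, 6.1 fixes who belongs in the final sample, and 8.1 describes how those criteria are checked. The 8.1 list says only what screening includes, and it also leaves out 6.1 items 4 and 5, so it is plainly not exhaustive. On that view the rules are cumulative, every entrant has chronic insomnia by the 6.1 definition, and the disputed group shrinks to people with that history but a low ISI. The screening form, recruitment script and HSDQ are attachments that are not shown and may settle the details. Entry on symptom frequency and duration is coherent, and nothing obliges a trial to set a cut-off on its outcome scale. The pilot's threshold does not bind this trial.

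Most of this stands. The cumulative reading is the more natural one, and the absence of an ISI floor is a design choice. Two further points are only missing detail: which HSDQ score the 4.0 means, and whether the screening ISI is also the baseline covariate (Table 3 lists ISI, but the baseline list in 10.1 does not). The sentence on not recruiting moderate-severe apnea may mean newly detected apnea only, since it follows the referral for treatment. The actigraph item is a wording slip unlikely to change enrolment.

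The objection does not remove the need to align the text. The cumulative reading is inferred, not stated. The ApneaLink statements differ on who is tested, the CPAP exception is in two places and absent from a third, and the actigraph question read literally contradicts 6.2. Whatever the attachments say, the protocol sections have to agree with them.

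**Conclusion.** The point holds as an internal contradiction in the eligibility text, at low severity. The rules decide who is enrolled and cannot all be followed as written.

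Three stronger readings are tempting, and the documents support none of them:

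- *The trial is underpowered or its sample size is wrong.* The sample size reproduces. The effect of low-ISI entrants is unknown, because neither their share nor their response is given. In the ranges shown, the adjusted analysis falls below 80% power at a 20% share only with no effect at all in these participants and a weak baseline correlation (77.8% at r = 0.3). A difference of 3 is the smallest the plan aims to detect, not its stated expectation. The ranges hold the residual SD fixed, and a sample of more mixed severity could have a larger one.
- *People with ISI of 7 or less cannot improve.* The pilot's treated arm ended at a mean of 6.94 with SD 5.27, so scores well below 7 occurred.
- *The plan must set an ISI floor.* An either-instrument rule may be deliberate. If so, it only needs to be stated.

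**What to change.** In one amendment:

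1. Reconcile 6.1, 6.2, 8.1, 10.1 and the screening form so that one insomnia rule applies. State whether the 6.1 history and the 8.1 scores are both required, whether ISI and HSDQ are joined by *and* or *or*, which HSDQ score the 4.0 means, and whether the screening ISI is the baseline covariate.
2. State one rule on who must have an ApneaLink result and how CPAP-treated apnea is handled. This review does not choose either rule.
3. Move the actigraph question to the list requiring YES, to match 6.2 item 6.
4. Report the number randomized with baseline ISI of 7 or less. Prespecify a supportive analysis: the same ANCOVA and permutation test, limited to baseline ISI above 7 and using the same pre-randomization ISI value as the covariate. Baseline precedes randomization, so the randomized comparison is kept. The primary analysis in all randomized participants is unchanged.

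The cost is wording plus one analysis of data already planned. If 10% to 20% are left out, 55 × 0.9 ≈ 49 or 55 × 0.8 = 44 per group remain, with power of about 94% or 92% for a difference of 3 at assumed r = 0.5. If the investigators decide to require ISI above 7 of everyone, and 10% to 20% of otherwise eligible people fall at or below 7 (assumed), screening rises from 316 to 316/0.9 = 351.1, rounded up to 352, or to 316/0.8 = 395.

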9.0 Recruitment Methods

N/A: This is a records review only, and subjects will not be recruited. NOTE: If you select this option, please make sure that all records review procedures and inclusion/exclusion screening are adequately described in other sections.

9.1 Describe when, where, and how potential subjects will be recruited.

NOTE: Recruitment refers to how you are identifying potential participants and introducing them to the study. Include specific methods you will use (e.g. searching charts for specific ICD code numbers, Research Participant Groups, posted advertisements, etc.).

Response:

Recruitment flyers (attached) will be distributed to institutions/organizations in WNY where participants are likely to be encountered like Cancer centers, community centers, Senior centers, VFW posts, etc. Study recruiters will review clinic schedules and prescreen medical records for cancer diagnosis, stage of disease and last treatment date to highlight potentially eligible participants for clinic staff. Clinicians involved in medical management of cancer survivors and their staff, will identify potential eligible participants, briefly explain the study, and obtain agreement from potential participants to be contacted. The PI or Study Coordinator will then contact the eligible participant to obtain their affirmative response of their interest in participating and then arrange to meet each potential participant in the clinic or at their home, if preferred. Additionally, given the shelter-in-place situation and some previous patients had difficulty returning to the clinic for the face-to face intervention, we will now offer the option of verbal consent and online teaching.

The following Research Participants Groups will be added: Buffalo Research Registry, Research Match, and i2b2. For i2b2, following IRB approval, the Institute of Healthcare Informatics team will provide contact information for the eligible participants. The provider will be contacted for approval using the Physician Permission Letter (draft letter attached). If the provider does not object, patients will be contacted by mail (draft letter attached) and then by telephone.

9.2 *Describe how you will protect the privacy interests of prospective subjects during the recruitment process.*

NOTE: Privacy refers to an individual's right to control access to him or herself.

Response:

Prospective eligible participants will only be approached by clinic staff regarding their interest in study participation. Only after eligible participants give consent to clinic staff will the PI or Study Coordinator screen the individual. Interested participants will be contacted in person or by telephone for the initial screening with study personnel (PI or Study Coordinator). If approached in person, eligible participants will be screened in a private clinic room with or without family members. Each subject in all phases of the study will be assigned a unique study identification number to be used on all data forms. All personally identifiable information will be kept strictly confidential. The HRP-611 Partial HIPAA Waiver has been added to document how privacy will be protected during the recruitment process for the new recruitment methods.

9.3 *Identify any materials that will be used to recruit subjects.*

NOTE: Examples include scripts for telephone calls, in person announcements / presentations, email invitations.

 *For advertisements, include the final copy of printed advertisements with your submission. When advertisements are taped for broadcast, attach the final audio/video tape. NOTE: You may submit the wording of the advertisement prior*

to taping to ensure there will be no IRB-required revisions, provided the IRB also reviews and approves the final version.

Response:

Insomnia Recruitment flyer attached. Eligibility Recruitment Script attached. Letter to eligible patients in i2b2 database attached. Research Match-Contact Message will be a recruitment flyer.

